6.3.3. Participant data

Participant confidentiality and welfare will always be maintained as the highest priority. Anyone with access to data, including the investigators, is subject to professional secrecy during and after the trial. We do not anticipate any sharing of data from this clinical trial with sites outside of the EU during the course of the project.

Anonymised data (health information, socio-demographic information, platform usage information) will not be deleted until the completion of the scientific analysis of the data plus the mandatory period for retaining clinical data (at least ten years in the UK).

6.3.4 Responsibility

The University of Exeter as sponsor of the trial is the data controller. The controller has the responsibility to ensure that the security and access arrangements for the database comply with the Data Protection Act (1998), and that all data processing and locally held personal data are registered with the host institution according to their employer's processes. Because this trial involves the

processing of personal information the Information Commissioner's Office (ICO), will be notified accordingly.

Legal data transfer agreements will be written and signed between the data controller and data processors prior to any participant being recruited, where appropriate. These agreements will be confirmation that the data processors will adhere to GDPR regulations, which protect and safely store participant personal and outcome data.

A common data protection and privacy policy authorised by the sponsor and the University of Exeter data protection team will be available on the study website. The screening website will also email this policy to consenting participants with the information sheet and consent form or provide it as a download.

6.3.5 Data Monitoring

Data will be accessed by the trial manager / data manager on the EXCTU data base on a regular basis (typically at least weekly) to check recruitment numbers and data quality and to monitor that all processes are working correctly. Detailed checks will occur early in the project to confirm that all systems are working properly. To download data the trial manager has to login via user name and password.

6.3.6 Breach of confidentiality

Occasionally records containing personal data that should not have been disclosed, e.g. an e-mail with a data file containing identifiable details may be received by a member of CTU staff or another staff member from an internal or external source. In such situations, the member of staff should contact the person who sent the data and make them aware of the breach of confidentiality. The records received should be either promptly deleted or any identifying details thoroughly erased. All suspected breaches should be investigated, documented in the study file and reported to the Sponsor as appropriate, following an established data breach the UNEXE procedure will be followed.

6.4 Trial documentation and archiving

The materials for the trial will be submitted with this study protocol.

Source documents, and trial-related electronic and other data will be stored safely and in accordance with the requirements of the UK GDPR and Data Protection Act (1998), no longer than legally required (for a minimum of ten years) or as stipulated by the Sponsor's requirements, and the applicable regulations and as per the Clinical Trial Units existing Business Continuity, Disaster Recovery & Archiving Standard Operating Procedures.

Data Access: Post-analysis, the final anonymised dataset will preferentially be stored in Open Research Exeter (ORE), the University of Exeter's open access repository.

Interoperability: Source data will be stored in Microsoft SQL server, formatted to maximise fidelity. This can be transposed and converted during the analysis stage into any format required. For the Open Research Exeter repository XML or CSV with a separate data dictionary is recommended.

Archiving: Items submitted to ORE will be retained indefinitely. ORE content is securely held on University of Exeter servers and regularly backed up according to current best practice. The ORE team will also try to ensure continued readability and accessibility of content, including the migration to new file formats where necessary.

Data archiving is described in further detail within the Data Management Plan.

6.5 Authorisation of participating site

The study is single site located at the University of Exeter. The site will be authorised after ethical approval has been given by the School of Psychology ethics committee and a data transfer agreement is in place with the UNEXE data controller. The trial manager will ensure the site is adequately staffed, staff researchers have access to a clinical adviser, and that site staff are familiar with the standard operating procedures, risk assessment procedures and that Good Clinical Practice (GCP) and General Data Protection Regulation (GDPR) standards will be followed.

6.6 Required documentation

Before recruitment can begin at sites, staff CV's and evidence of good clinical practice and GDPR training will be collected. Each site will be provided with copies of the standard operating procedures for the trial. Each site will create a resource of online links and local and national services for those indicating that they have current depression, suicide risk, mania and psychosis. These links will be checked before the trial starts and at monthly intervals during recruitment to ensure that these details are kept up to date.

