8.11 Long term follow-up assessments

Participants will be followed up at 6 and 12 weeks post baseline.

Table 9 Procedures schedule

Procedures	Screening	Baseline	6 weeks post- baseline follow-up	12 weeks follow-up
Informed consent	Yes	Yes	No	Yes
Demographics	Yes	No	No	No
Mental Health History	Yes	No	No	No

Eligibility assessment	Yes	No	No	No
Randomisation	No	Yes	No	No
Access to intervention	No	Yes	Yes	Yes
Assessment of wellbeing and depression	Yes	Yes	Yes	Yes
Assessment of current functioning	No	Yes	Yes	Yes
Feasibility outcomes	No	No	No	Yes
Adverse event assessments	No	No	Yes	Yes

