12.2 Planned recruitment rate

Recruitment of 120 participants into the study across two iterations of intervention delivery (Cohort 1=30 SbRI; 30 DLT; Cohort 2=30 SbRI; 30=DLT) will take place over 28 weeks (June 2023 to December 2023) (originally 1/9-22 to 13/3/23 within a single study site (University of Exeter). Recruitment rate within this timeframe represents a feasibility outcome.

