14.3.2 Assessment Website at Follow-up (6 and 12 weeks)

A recruit may indicate risk on the assessment website in follow-up assessments in response to questions about suicidality. If the participant scores 1-3 on question 9 of the PHQ9, then further questions to assess risk will automatically be presented.

PHQ9; Q9

Over the last two weeks, how often have you been bothered by any of the following problems? Thoughts that you would be better off dead, or of hurting yourself in some way?

Those scores would represent the answers several days (1), more than half the days (2) and nearly every day (3)

The further risk questions which will automatically be asked:

R1 In the last 2 weeks have you been experiencing regular thoughts about suicide?

R2 In the last 2 weeks have you had any intention to hurt or kill yourself?

R3 In the last 2 weeks have you made any plans to harm yourself or end your life?

If the participant answers yes to any of those questions then they would be automatically presented with the following risk page:

Follow up Website Automated Risk Message:

"Your responses to these questions suggest you have been thinking about suicide or about hurting yourself.

These kinds of thoughts can vary a lot. This may have just been a brief passing thought or reflect a sense of feeling trapped, but without any intention to do anything. These thoughts are relatively common and not that unusual in people who feel stressed. If you would like support with these thoughts, please contact your GP or relevant medical professional;

If you feel at high risk to yourself or others, please contact your GP immediately.

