- Papyrus [name] or text: [name] offers National support to young people up to age 35 who are feeling suicidal. (Monday-Friday 10:00am-5:00pm and 7:00pm-10:00pm; 2:00pm-5:00pm on weekends, [contact]
- The Samaritans [name] Freephone (UK and Republic of Ireland): [name] (24 hours), offer a confidential service so you can talk about your feelings, you can contact them at www.samaritans.org, Email: [contact]
- **SANE** offers support to anyone coping with mental illness, including concerned relatives or friends. The SANE helpline **[name]** is available 7 days a week from 6.pm-11 pm
- Maytree is a registered charity supporting people in suicidal crisis and is open for calls and emails 24 hours a day. [name], [contact]
- Young Minds Crisis Messenger provides free, 24/7 crisis support across the UK if you are experiencing a mental health crisis. If you need urgent help text YM to [name]. Texts are free from EE, O2, Vodafone, 3, Virgin Mobile, BT Mobile, GiffGaff, Tesco Mobile and Telecom Plus.
- **CALM [name]** (Daily 17:00-midnight) Offers support to young men in the UK who are down or in a crisis, www.thecalmzone.net
- The Mix, Freephone: [name] (13:00-23:00 daily), If you're under 25 you can talk to The Mix for free on the phone, by email or on their webchat. You can also use their phone counselling service, or get more information on support services you might need. www.themix.org.uk

If you would like further advice on these issues from the team, you can contact us by submitting the form below to send an email.

We note that the research team are not clinicians and cannot provide therapy. However, we can guide you in accessing help, for example, by contacting your GP, which is why we ask for GP details. The team are only available during normal working hours, Monday to Friday and may take 1 or 2 working days to respond.

FORM TO SUBMIT

Name Address Phone number GP Name GP Phone number GP Address

In the event that a participant indicates suicide risk at follow up and this screen is displayed, an automated report/record from the website will be sent to the therapists and chief investigator and will be logged by them and the trial manager. The record will show the trial number and the answers to the 3 risk questions (e.g., R1=Y, R2=N, R3=N). This data will monitor frequency of suicidality across the trial arms.

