- Young Minds Crisis Messenger provides free, 24/7 crisis support across the UK if you are experiencing a mental health crisis. If you need urgent help text YM to [name]. Texts are free from EE, O2, Vodafone, 3, Virgin Mobile, BT Mobile, GiffGaff, Tesco Mobile and Telecom Plus.
- **CALM [name]** (Daily 17:00-midnight) Offers support to young men in the UK who are down or in a crisis, www.thecalmzone.net
- The Mix, Freephone: [name] (13:00-23:00 daily), If you're under 25 you can talk to The Mix for free on the phone, by email or on their webchat. You can also use their phone counselling service, or get more information on support services you might need. www.themix.org.uk

Talking to people who understand can make it much easier to manage your symptoms so **please do call your GP or one of the specialist helplines above**.

14.5 For participants reporting significant levels of depression at any of the follow-up assessments (defined as PHQ-9 score >20)

The follow-up website will automatically provide them with the following information:

Follow-up Website Automated message for depression:

"Your responses to these questions suggest that within the last month, your overall mood has been low for at least 2 weeks and has had a negative effect on your life. It may be that you are currently experiencing an episode of depression or going through a period of stress or loss.

If you currently are having problems with the symptoms of depression then we strongly recommend that you talk to your general practitioner, family doctor or a mental health professional about your difficulties, as he or she may be able to find ways to help you to improve your mood and handle life's difficulties better.

If you have not had a health check recently that may also be worth doing so. If you have a diagnosis of depression, please make sure that you follow your treatment regime and consult with the medical professionals involved in your care.

You can contact your GP using the normal telephone number for your GP practice. If the surgery is not open, you will either be re-directed automatically to the out-of-hours GP service or you will be given another number to call. You can also **phone 111 to access the NHS 111 service**, which provides access to local NHS healthcare services in England, and is available 24 hours a day, 365 days a year.

As well as your GP, there are many other services available who are really experienced at helping people with your symptoms:

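### The monthly check of support links stops when recruitment ends, but the automated risk and depression pages that list such links are still shown at later 6- and 12-week follow-ups

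*Protocol*

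**What the plan says.** Section 6.6 requires a resource of "online links and local and national services for those indicating that they have current depression, suicide risk, mania and psychosis". It then fixes when the resource is checked. The links are to be "checked before the trial starts and at monthly intervals during recruitment to ensure that these details are kept up to date".

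The resource is not described as being for screening only, and pages of this kind are not confined to screening. Section 8.11 states: "Participants will be followed up at 6 and 12 weeks post baseline". At those assessments two automated pages can appear:

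- **Suicide risk (14.3.2).** A PHQ-9 item 9 score of 1 to 3 brings up three further questions. "If the participant answers yes to any of those questions then they would be automatically presented with the following risk page". The page lists helplines, text services, opening hours and web addresses, for example: "Maytree is a registered charity supporting people in suicidal crisis and is open for calls and emails 24 hours a day".
- **Depression (14.5).** For a follow-up PHQ-9 score above 20: "The follow-up website will automatically provide them with the following information". This page lists websites and helplines.

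On timing, section 12.2 says that recruitment of 120 participants in two cohorts of 60 "will take place over 28 weeks (June 2023 to December 2023"). The study summary (section 5, Table 7) gives 28 weeks for a different span, from the first group session to the final follow-up.

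**The concern.** The protocol itself treats monthly checking as needed to keep these details current, and it gives no reason why that need should end with recruitment. As written, the check stops while randomised participants can still be sent to the pages after reporting suicidal thoughts or severe symptoms. A changed telephone number, altered opening hours or a dead link could then go unnoticed for up to 12 weeks after the last participant's baseline.

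The pages carry weight in this trial. Section 14.1.2 explains that GP details are not routinely held, so the default response to a possible clinical problem is information and signposting given directly to the participant. Section 14.3.2 adds that the team works normal hours and may take one or two working days to reply.

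This is a matter of safety procedure. It has no bearing on the sample size, error rates or analysis.

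**Working it through.** The protocol gives no figure on this point, so there is nothing to reproduce. The check is one of timing.

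**Inputs**
- Participants: N = 120 (Table 7; 12.2).
- Follow-ups: 6 and 12 weeks after baseline (8.11), so 120 × 2 = 240 planned assessments.
- Recruitment: 28 weeks, two cohorts of 60 (12.2).
- Alternative span: 28 weeks from first group session to final follow-up (Table 7).

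**Assumptions (not in the protocol):** no attrition; baseline at entry; entry patterns as stated in each case. Table 9 also lists measures for control participants after they move to the intervention; these are not counted.

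**Whether a gap exists.** The last person recruited has a 12-week assessment 12 weeks after baseline. If recruitment means enrolment, some follow-up falls after the check has stopped under any entry pattern.

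**How large it is.** With even entry over R weeks, the share of f-week assessments that fall after recruitment closes is f/R.

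*Case A: even entry over R = 28 weeks (12.2 taken literally)*
- 6-week: 6/28 = 21.4%; 120 × 6/28 = 25.7
- 12-week: 12/28 = 42.9%; 120 × 12/28 = 51.4
- Total: 25.7 + 51.4 = 77.1; 77.1/240 = 32.1%

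*Case B: second cohort of 60 recruited just before its group session, at the close of recruitment, with the first cohort's follow-up already complete*
- 60 × 2 = 120; 120/240 = 50%

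*Case C: the 28 weeks include final follow-up (Table 7), with even entry*
- Recruitment must end by week 28 − 12 = 16, so R = 16
- 6-week: 6/16 = 37.5%; 120 × 6/16 = 45
- 12-week: 12/16 = 75%; 120 × 12/16 = 90
- Total: 45 + 90 = 135; 135/240 = 56.25%

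*Case D: recruitment in 6.6 and 12.2 loosely means the whole 28-week trial*
- Checks would continue to the last follow-up, and the share is near zero.

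Case B rests on the two cohorts of section 12.2. Sections 8.6 and 9.1 give other numbers of iterations (six and three), so the entry pattern is itself not settled.

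**The case against.** **Recruitment may mean the whole trial.** Sections 5 and 12.2 attach the same 28 weeks to different spans. If 12.2 means the whole trial, the gap almost disappears. This is possible but weak: the sentence in 6.6 itself distinguishes the start of the trial from recruitment, and recruitment does not ordinarily include follow-up. What stands is that the low end of the range is near zero, and that the two 28-week statements need reconciling.

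**The figures do not count people affected.** This stands. The risk page needs a positive item 9 and then a yes to one of three questions; the depression page needs a PHQ-9 score above 20. Table 8 admits only participants with PHQ-9 and GAD-7 scores of 9 or below. The protocol gives no rate of alerts and none for changes in the listed services.

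**The page is not the only safeguard.** This also stands. Under 14.1.2 alerts are logged, the research officer, trial manager and chief investigator are told, and a clinician may contact the participant. Under 14.3.2 an automated report goes to the therapists and chief investigator. Both pages also point to the participant's own GP and NHS 111, and the risk page adds A&E and family or friends. Several independent services are listed, so one stale entry would not remove every route to help. None of these safeguards, however, keeps the page accurate, and staff contact may not be immediate.

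**Section 6.6 does not expressly name the follow-up pages.** True. The link rests on its reference to current depression and suicide risk. But if 6.6 does not cover those pages, no section provides for checking them at all, so this reading does not close the gap.

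A reader might infer that a third to a half of participants would be given out-of-date crisis information, or would be left without help. The documents support neither: the shares describe when assessments fall, under assumed entry patterns.

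**Conclusion.** The point holds as a minor but real gap in participant safety. The rule in 6.6 fixes an end date for the link check that is earlier than the end of the period in which the follow-up pages in 14.3.2 and 14.5 can appear. This is a stated rule that stops too soon, not a detail left to another document.

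Between about 32% and 56% of the 240 planned follow-up assessments would fall outside the check, depending on the entry pattern, and close to none if recruitment is read as the whole trial. That the gap exists depends only on recruitment meaning enrolment; its size depends on the assumptions listed. Actual harm would need an alert, a listed service that had changed, and failure of the other routes to help. The protocol allows none of these to be quantified.

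**What to change.** In section 6.6, replace the limit to the recruitment period with wording that runs the monthly check until the last participant has completed the final follow-up assessment. State that the check covers the follow-up pages in 14.3.2 and 14.5 as well as the screening pages. When making the edit, reconcile the two uses of 28 weeks in Table 7 and section 12.2 so that the end of the checking period can be dated.

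The cost is about three further monthly checks by existing staff, since 12 weeks is roughly three months. No treatment, risk threshold, assessment or analysis changes.

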7. PARTICIPANT INCLUSION/EXCLUSION CRITERIA

Table 8 Inclusion/Exclusion criteria

Inclusion	Exclusion
Aged 16 or over.	AGED 16<
PHQ9=<9; GAD7=<9	PHQ9>9; GAD7>9
Suicide risk: PHQ9; Q9=<1 and R2=No and R3=	Suicide risk: PHQ9; Q9>1 and R2=Yes and/or R3
No	=Yes
Resident in UK	
Student at the University of Exeter	Past history of psychosis, mania,
	substance/alcohol dependence

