8.12 Withdrawal criteria

Participants can choose whether they want to stop using the sbLICBT intervention, or if they want to withdraw from the trial completely (including all assessments) at any time. Participants will also be withdrawn from the trial if the site clinical advisor, or the participant's medical practitioner advises that this is best for their wellbeing. A log will be kept of the participant number, reason for and date of all withdrawals from the trial. Participants who met the inclusion and exclusion criteria at baseline will not be replaced. Participants who did not meet the criteria at baseline can be replaced and their data removed from the data set. Participants who withdraw from the trial will not be followed up. Once a participant withdraws, all email and text notifications that are set on auto will be removed.

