13. ADVERSE EVENTS

13.1 Participant welfare and safety

There is no known health risk associated with any of the assessments or the sbLICBT self-help intervention. The risk concerning participation in this study is believed to be low. Further, we anticipate that the self-help will reduce vulnerability and the risk for developing poor mental health and improve well-being and resilience. In our experience from previous projects, participants are happy to participate and enjoy the assessment tasks. We will strive to use tasks that the participants experience as motivational and reinforcing whenever possible. This will also ensure a low attrition rate.

Because the trial is enhancing resiliency and prevention of poor mental health, the initial screening process will exclude anyone with history of severe psychiatric disorder and those reporting elevated suicidality. These individuals will be automatically guided towards appropriate information and sources of help. This process means that individuals likely to have significantly increased risk (e.g., for self-harm and suicidality), and/or for whom more intensive psychological and psychiatric treatment is appropriate, will not be included in the study.

Other than the intervention failing to produce an effect, there is nothing in the literature to suggest possible adverse effects of the assessments and interventions for the young people involved. Versions of components within the intervention have been previously used with no detected harmful effect.

As with all psychological interventions, individuals reflect on their difficulties, which can produce temporary increases in distress, but no more than would commonly occur in daily life. Prior work has provided positive feedback on the sbLICBT self-help intervention and indicated enhanced resiliency, with no serious adverse events reported: as such, the intervention within the trial may benefit individual participants. The likeliest outcome for users who do not find the intervention of benefit is their disengagement from it. In addition, all participants receive more intensive monitoring, with processes to identify and direct all relevant participants to potential sources of help.

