14.1.1 Risk management during pre-screening

In response to recommendations from our ethical review boards we have now added a pre-screening section to our assessment to allow those with experience of, or symptoms of depression to access help pages linking to sources of support as soon as possible. Participants are given the following automated paragraph and options:

Pre-screening website automated message:

This study aims to examine the effectiveness of a written strength-based intervention based on Cognitive Behavioural Therapy to enhance resiliency in young people that are currently well. If you are currently struggling with depression, traumatic experiences, or suicidal thoughts then the trial would not be right for you and specialist help would be the best option. If these issues are affecting you now then we would urge you to reach out to family, friends, or your family doctor/general practitioner. Click the relevant button to below for some links to relevant helpful information and support services available to you.

- I would like to learn what depression is
- I am having suicidal thoughts at the moment
- I have depression now
- I have experienced a traumatic experience in the last month
- I do not have depression or experienced a traumatic experience in the last month and would like to take part in the trial
- I do not want to take part

Each of the options is linked to help pages. If participants access the help pages on current depression, or risk then they are excluded from the trial. Their contact details have not been taken at that stage so they cannot be contacted.

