14.3.1 EDC Website at Screening

A recruit may indicate risk on website during the screening phase of the baseline assessment in response to questions about suicidality. If the participant scores 1-3 on question 9 of the PHQ9, then further questions to assess risk will automatically be presented.

PHQ9-Q9

Over the last two weeks, how often have you been bothered by any of the following problems? Thoughts that you would be better off dead, or of hurting yourself in some way?

Those scores would represent the answers several days (1), more than half the days (2) and nearly every day (3)

The further risk questions which will automatically be asked:

R1 In the last 2 weeks have you been experiencing regular thoughts about suicide?

R2 In the last 2 weeks have you had any intention to hurt or kill yourself?

R3 In the last 2 weeks have you made any plans to harm yourself or end your life?

If the recruit answers yes to any of those questions then they would be excluded from the trial and would be automatically presented with the following risk page:

EDC Screening Website suicide risk automated message:

"Your responses to these questions suggest you have been thinking about suicide or about hurting yourself.

These kinds of thoughts can vary a lot. This may have just been a brief passing thought or reflect a sense of feeling trapped, but without any intention to do anything. These thoughts are relatively common and not that unusual in people who feel stressed. If you would like support with these thoughts, please contact your GP or relevant medical professional.

If you feel at high risk to yourself or others, please contact your GP immediately.

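### The suicide-risk criterion in Table 8 (section 7) leaves out R1, on which section 14.3.1 excludes, and its exclusion column is not the complement of its inclusion column

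*Protocol*

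**What the plan says.** Table 8 in section 7 has an inclusion and an exclusion column. (Section 9.1 has another table numbered 8; it is not meant here.)

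- **Inclusion:** "Suicide risk: PHQ9; Q9=<1 and R2=No and R3", with the answer No completing the line.
- **Exclusion:** "Suicide risk: PHQ9; Q9>1 and R2=Yes and/or R3", with the answer Yes completing the line.

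R1 is in neither column.

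Section 14.3.1 describes the screening website.

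- **When the risk questions open:** "If the participant scores 1-3 on question 9 of the PHQ9, then further questions to assess risk will automatically be presented".
- **What is asked:** R1 ("R1 In the last 2 weeks have you been experiencing regular thoughts about suicide"), R2 (intention) and R3 (plans).
- **The rule:** "If the recruit answers yes to any of those questions then they would be excluded from the trial".

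Three other places bear on the point.

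- **Section 13.1** gives the aim: "the initial screening process will exclude anyone with history of severe psychiatric disorder and those reporting elevated suicidality".
- **Section 14.1.1** adds an earlier filter: "If participants access the help pages on current depression, or risk then they are excluded from the trial".
- **Section 8.12** attaches a consequence to eligibility: "Participants who did not meet the criteria at baseline can be replaced and their data removed from the data set".

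**The concern.** The formal eligibility table and the automated screen use different items for the same safety criterion. A student who reports regular thoughts of suicide but no intention or plan, and scores 1 on Q9, passes one and fails the other. In addition, the exclusion column requires a high Q9 score together with a yes on R2 or R3, whereas the logical opposite of the inclusion rule needs only one of these.

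Three things depend on having one rule:

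- who is admitted, given the stated aim of screening out elevated suicidality;
- the number screened out with reasons, which is a listed feasibility outcome (section 10.1), feasibility being the primary analysis (section 12.5);
- who may be replaced and have data removed under section 8.12, or be withdrawn as ineligible under section 12.4.

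**Working it through.** The protocol gives no figure to reproduce. The check enumerates the possible answers and applies each rule as written.

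**Inputs.** Q9 is scored 0 to 3. R1 to R3 are yes/no and are asked only when Q9 is 1, 2 or 3 (section 14.3.1). That gives 3 × 2 × 2 × 2 = 24 patterns. Q9=0, with no risk questions asked, is a 25th pattern; it meets inclusion and is not in dispute.

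**Rules.**

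- Table 8 inclusion: Q9≤1 and R2=No and R3=No.
- Table 8 exclusion, reading A (the natural one): Q9>1 and (R2=Yes or R3=Yes).
- Table 8 exclusion, reading B: (Q9>1 and R2=Yes) or R3=Yes.
- Section 14.3.1 exclusion: R1=Yes or R2=Yes or R3=Yes.

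| Answers | Patterns | Meets inclusion | Excluded, A | Excluded, B | Excluded by 14.3.1 |
|---|---|---|---|---|---|
| Q9=1; R1, R2, R3 all No | 1 | 1 | 0 | 0 | 0 |
| Q9=1; R1=Yes; R2=R3=No | 1 | 1 | 0 | 0 | 1 |
| Q9=1; R2 or R3=Yes | 6 | 0 | 0 | 4 | 6 |
| Q9=2–3; R1, R2, R3 all No | 2 | 0 | 0 | 0 | 0 |
| Q9=2–3; R1=Yes; R2=R3=No | 2 | 0 | 0 | 0 | 2 |
| Q9=2–3; R2 or R3=Yes | 12 | 0 | 12 | 12 | 12 |
| **Total** | **24** | **2** | **12** | **16** | **21** |

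**Results.**

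1. *Direct conflict.* One pattern meets the table's inclusion rule and is excluded by 14.3.1: Q9=1, R1=Yes, R2=R3=No (second row). The separate limit of 9 on the PHQ-9 total does not remove it, because a total of 9 or less can contain Q9=1.
2. *Columns not complementary.* In neither column: 24 − 2 − 12 = 10 on reading A, and 24 − 2 − 16 = 6 on reading B. No pattern is in both columns. On reading A the 10 include all six with Q9=1 and stated intention or plans. Section 14.3.1 excludes 8 of the 10 (6 + 2), or 4 of the 6 on reading B (2 + 2).
3. *Mismatch in the other direction.* The remaining two patterns, Q9=2 or 3 with all three risk questions No, are barred only by the Q9 limit in the table's inclusion column. Section 14.3.1 states no exclusion for them.
4. *Bound on harm.* Of the 6 + 12 = 18 patterns with R2 or R3=Yes, the table includes none and 14.3.1 excludes all 18.
5. *Proposed rule* (include if Q9≤1 and R1=R2=R3=No; otherwise exclude): 1 of the 24 included, 23 excluded, none unclassified and none in both columns. Adding the Q9>1 limit to 14.3.1 makes its count 21 + 2 = 23, the same set.

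**The case against.** The best defence is that the two sections can be read cumulatively: a student must meet Table 8 and trigger no exclusion in 14.3.1. Screening is automated at one site, so the conflict pattern would be shown the risk page and turned away. Table 8 is evidently not the only list of exclusions, since 14.1.1 adds another. Every pattern in neither column fails inclusion, so the loose 'and' misclassifies nobody, and a limit need not be repeated in a second section to apply. Finally, R1 may have been left out of the table on purpose, to admit students with thoughts but no intention or plan.

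Much of this stands as a limit on the consequences. If the website works as 14.3.1 describes, the conflict pattern is never randomised, and the section 8.12 consequence arises for it only if the system was built to the table. The exclusion-column fault is one of drafting.

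It does not remove the contradiction. The cumulative reading yields exactly the rule proposed here, but a reader of Table 8 alone would not reach it, and the protocol does not say which text the electronic system was programmed from. Dropping R1 from 14.3.1 would also end the conflict, and only the sponsor can confirm what was intended. Section 13.1 does not define elevated suicidality, so it does not settle the matter alone. The rest of the text nevertheless points towards adding R1 to the table: the pre-screen in 14.1.1 diverts people with current suicidal thoughts, and 14.3.2 uses R1 yes with R2 and R3 no as its sample record of a participant indicating suicide risk.

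**Conclusion.** The concern holds and should be fixed. Table 8 and section 14.3.1 disagree outright on 1 of 24 answer patterns. The table's columns leave 10 patterns (6 on the other reading) unassigned, and two patterns are barred in one section only. These are counts of answer combinations, not of students. The protocol gives no frequencies, so the number of students affected is unknown.

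The safety effect is limited. Neither rule admits anyone with stated intention or plans, the pre-screen removes those who open the risk help page, and risk arising in the trial is logged and followed up. Sample size and error rates are unaffected. What is wrong is that a safety eligibility rule has two meanings, while the count of screened-out students and any replacement with data removal depend on it. The conclusion rests on the wording alone and holds under either reading of the exclusion column.

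**What to change.** In Table 8 of section 7:

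- **Inclusion:** Q9=<1 and R1=No and R2=No and R3=No (R1 to R3 are not asked when Q9=0).
- **Exclusion:** Q9>1 or R1=Yes or R2=Yes or R3=Yes.

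State the same rule in section 14.3.1, including the Q9>1 limit. Adding R1 to the table alone would leave the two Q9=2 or 3, all-No patterns unmatched. Then test the electronic screening logic against the 24 patterns and Q9=0.

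The cost is one table row, one sentence and one logic check, with no change to design, sample size or assessments. The drawback is that students with regular suicidal thoughts but no intention or plan are screened out, which 14.3.1 already does. If the sponsor did mean to admit them, 14.3.1 should be changed instead and the reason given.
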